4.1. Treatment Misallocations

[figure not shown]
All analyses will be performed on an "as-treated" basis and will not include data from participants who are enrolled but not treated.

If a participant takes a treatment that is not consistent with the assigned treatment, for example, takes a dose level inconsistent with the assigned cohort, then the participant will be reported under the treatment label that he actually received for all analyses, where applicable. A separate listing will be compiled to indicate the actual dose level and the nominal dose received, where applicable.

4.2. Protocol Deviations

A full list of protocol deviations will be compiled and reviewed to identify major and minor deviations prior to database closure.

5. GENERAL METHODOLOGY AND CONVENTIONS

5.1. Hypotheses and Decision Rules

There is no formal hypothesis testing in this study according to the original design of this FIH study. Because the study has a relatively small sample size and is not designed to have sufficient power to detect treatment differences, it is expected that hypothesis testing is not likely to reach statistical significance unless there is dramatic treatment effect. Nominal p-values will be presented. The 95% CI for the change from baseline in secondary (dystrophin expression/distribution)

5.2. General Methods

the subgroup.

Bootstrap to estimate the parameter of interest

Given the relatively small sample size of this study and the variability of the various outcome parameters, the non-parametric bootstrapping method (Efron 1979², Efron 1993³) will be used to compute the $100(1-\alpha)$ % CIs of the parameters of interest for robust evaluation without underlying distributional assumptions. Specifically, the sampling distributions of the statistics derived from 10,000 bootstrap samples such as the mean of the change from baseline in an endpoint will be used to construct the 95% CI of the mean when $\alpha = 0.05$.

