2.3. Secondary Estimand(s)

Analyses of the secondary endpoints by population (ambulatory, non-ambulatory, overall) and by dose cohort are described in Section 6.2. For each secondary endpoint, the four attributes associated with the estimand are summarized below.

- Population: Among ambulatory and non-ambulatory participants who meet the inclusion and exclusion criteria, those who receive a single IV infusion of fordadistrogene movaparvovec.
- Variable: Secondary endpoints listed in Section 2.1.

- Intervention effect: Effect of treatment on dystrophin/mini-dystrophin expression and distribution through 1 year post-treatment, regardless of adherence to background and protocol-mandated glucocorticoid regimens.
- Population-level summary: Changes from Baseline (pre- and post-) for treatment difference through 1 year post-treatment

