2.5. Study Design

This FIH/FIP study is an open-label, multi-center, ascending dose study designed to evaluate the safety and tolerability of a single IV infusion of fordadistrogene movaparvovec in

participants with DMD. There are 22 participants who received a single dose of fordadistrogene movaparvovec between 1E14 vg/kg and 3E14 vg/kg per the ITR-based method or 2E14 vg/kg per the TG-titer method.

Fordadistrogene movaparvovec at 3E14 vg/kg per the ITR-based titer method is approximately equivalent to 2E14 vg/kg per the TG-titer method. Therefore, participants dosed at 3E14 vg/kg per the ITR-based titer method or at 2E14 vg/kg per the TG-titer method will be grouped in the high dose cohort.

- 1. Ambulatory low dose cohort (N=3): 1E14 vg/kg based on the ITR method
- 2. Ambulatory high dose cohort (N=16): 3E14 vg/kg based on the ITR method or 2E14 vg/kg based on the TG method
- 3. Non-ambulatory high dose cohort (N=3): 2E14 vg/kg based on the TG method
 - Sirolimus non-ambulatory high dose cohort (N=1): 2E14 vg/kg per the TG-based titer method.

Note that a safety profile will be provided for the one participant who received sirolimus. No other summaries will be provided since only one participant received sirolimus.

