4. ANALYSIS SETS (POPULATIONS FOR ANALYSIS)

Data for all participants will be assessed to determine if the participants meet the criteria for inclusion in each analysis population prior to releasing the database.

For purposes of analysis, the following populations are defined:

Population	Description	
Enrolled	All subjects who sign the informed consent document.	
FAS	All enrolled participants who receive fordadistrogene	
	movaparvovec. Analyses will be performed on the FAS	
	population unless otherwise specified.	
Safety	All enrolled participants who receive fordadistrogene	
	movaparvovec. Participants will be analyzed according to	
	intervention they actually received.	
Pharmacodynamic	All participants in the FAS who have baseline and at least	
Analysis Set	one post-dose mini-dystrophin parameters of interest reported.	

Population	Description
Ambulatory	All participants in the FAS who meet the study eligibility
	criteria for ambulatory status at enrollment: able to walk 10
	meters unassisted and rise from floor within seven seconds.
Non-ambulatory	All participants in the FAS who meet the study eligibility
	criteria for non-ambulatory status at enrollment: unable to walk
	10 meters unassisted.
Low dose cohort	All participants in the FAS who receive 1E14 vg/kg per the
	ITR-based method.
High dose cohort	All participants in the FAS who receive 3E14 vg/kg per the
	ITR-based method or 2E14 vg/kg per the TG-based titer
	method.
CCI	
Non-sirolimus cohort	All participants in the FAS who do not receive sirolimus within
	2 weeks before and after fordadistrogene movaparvovec
	infusion.
Regardless of adherence to	All participants in the FAS, regardless of adherence to
glucocorticoid regimen	background or protocol-mandated glucocorticoid regimens.

The term "ambulatory status at baseline" will be used to describe the stratification factor (ambulatory versus non-ambulatory) used to partition the study participants and report the corresponding group results. The term "overall" will be used to refer to all participants in the FAS.

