6.2. Secondary Endpoint(s)

Quantification of the expression and distribution of mini-dystrophin detected by LC-MS and the immunofluorescence assay can provide evidence of expression of the transgene product. To limit possible variability by averaging or comparing results from different sections of a given muscle biopsy tissue, only sectioned tissue with results from each of the planned assays will be included in the summary.

The bootstrapping method (Efron 1979²) will be used to compute the 95% CIs of the parameters of interest for robust evaluation without underlying distributional assumptions.

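### Read as a percentile interval, the planned 95% bootstrap CI is only the sample minimum and maximum in the N=3 groups (coverage at most 75%), and no visible SAP text withholds it there

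*SAP*

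**What the plan says.** SAP 5.2 (General Methods) chooses a non-parametric bootstrap because the study is small. For a 95% interval it uses "the sampling distributions of the statistics derived from 10,000 bootstrap samples such as the mean of the change from baseline in an endpoint". No interval type (percentile, basic, BCa, studentised) is named. SAP 6.2 carries the method to the secondary endpoints, where it "will be used to compute the 95% CIs of the parameters of interest for robust evaluation without underlying distributional assumptions".

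The grouping is in SAP 2.3: "Analyses of the secondary endpoints by population (ambulatory, non-ambulatory, overall) and by dose cohort are described in Section 6.2". SAP 2.5 gives the group sizes. Two of them are three:

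- "Ambulatory low dose cohort (N=3): 1E14 vg/kg based on the ITR method"
- "Non-ambulatory high dose cohort (N=3): 2E14 vg/kg based on the TG method"

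The number with usable paired biopsies can be lower. The Pharmacodynamic Analysis Set (SAP 4) is "All participants in the FAS who have baseline and at least" one post-dose value. SAP 6.2 adds that "only sectioned tissue with results from each of the planned assays will be included in the summary". The protocol (Figure 2 footnote and 7.6) also allows fewer biopsies in non-ambulatory subjects.

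The visible small-group rule in SAP 6.2.1 and 6.2.2 concerns plots: a group of three or fewer is shown as points instead of a box plot. Two relevant places are incomplete in the public text. SAP 5.1 breaks off after "The 95% CI for the change from baseline in secondary (dystrophin expression/distribution", and SAP 5.2 opens with the tail of a sentence about a subgroup.

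**The concern.** The SAP presents the bootstrap as robust in small samples. With three values that reason fails. Resampling three numbers can only rearrange those numbers, so the resampled means cannot reach beyond the observed range, however wide the true uncertainty is.

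The two groups affected are where data are thinnest. The low-dose cohort is one side of any comparison of expression between doses, and the three non-ambulatory participants are the only data for that population. An interval labelled 95% would overstate how well the mean change is known in both.

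**Working it through.** **Inputs.** Nominal level 95%, 10,000 resamples, statistic = mean change from baseline (SAP 5.2). Group sizes 3, 16 and 3, giving 19 ambulatory and 22 overall (SAP 2.5). The documents give no outcome distribution, so those used below are assumptions.

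**The plan's own figure.** Alpha = 0.05 gives a nominal level of 1 − 0.05 = 95%. The question is whether the method delivers it at n=3.

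**Step 1: where the percentile limits fall.** Three values give 3³ = 27 equally likely resamples. One of them repeats the smallest value three times, so the lowest possible mean has probability 1/27 = 3.7%. This exceeds 2.5%, so the 2.5th percentile is the sample minimum. By symmetry the 97.5th percentile is the sample maximum.

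Random resampling does not change this. Of 10,000 resamples about 10,000/27 = 370 equal the minimum, against the 250 needed. The SD of that count is √(10,000 × 1/27 × 26/27) = 18.9, so 250 lies 6.4 SD below it. In 5,000 simulated data sets with 10,000 resamples each, the limits were the minimum and maximum every time.

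**Step 2: coverage.** Let p be the chance that one value falls below the true mean. The interval misses only if all three values fall on the same side:

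coverage = 1 − p³ − (1 − p)³ = 3p(1 − p)

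- Symmetric outcome, p = 0.5: 3 × 0.5 × 0.5 = **75.0%**, the maximum for any continuous outcome.
- Lognormal, sigma 0.5: p = Φ(0.25) = 0.599, giving **72.1%**.
- Lognormal, sigma 1.0: p = Φ(0.5) = 0.691, giving **64.0%**.

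**Step 3: other interval types at n=3, normal data.**

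| Type | Coverage |
|---|---|
| Percentile | 75% (exact) |
| Basic | 75% |
| Normal approximation with bootstrap SE | 75% |
| BCa | 68–72%, depending on how ties are counted |
| Bootstrap-t, equal-tailed | 81% |
| Bootstrap-t, symmetric | 93% |
| Student t, for reference | 95% |

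The normal-approximation figure has a closed form. The bootstrap SE is the usual one times √(2/3), so the multiplier is 1.96 × 0.8165 = 1.600, and P(|t₂| < 1.600) = 0.749. The t interval uses 4.30 and is about 2.6 times as wide as the percentile interval.

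**Step 4: excluding zero.** If the change can take either sign and is symmetric about zero under no effect, the interval excludes zero when all three changes share a sign: 2 × (1/2)³ = 25%, against a nominal 5%.

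**Step 5: larger groups.** Simulated percentile coverage under normal data is 92.5% at N=16, 92.6% at N=19 and 92.6% at N=22. Under lognormal data with sigma 1.0 it is about 84–86%.

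**The case against.** The strongest objection is that the governing text cannot be read. The fragment that opens SAP 5.2 looks like the end of a small-subgroup rule, so such a rule probably exists. A reader might infer that the SAP has none; the documents do not support that. The amendment history only hints at the threshold. The logged version 5 wording replaces summaries with individual profiles below three participants, which would let n=3 through. The version 5 rationale speaks of non-ambulatory subjects with n ≤ 3. The version 6 change list, as far as it can be read, records no change to the rule. Current thresholds elsewhere (SAP 6.1.2 and 6.1.6) treat three participants as enough for a summary or an interval. This leans towards an interval being printed at n=3 but does not prove it. Both logged wordings cover n=2, so the 50% coverage ceiling there should not be held against the plan.

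Second, no single visible sentence orders an interval for a group of three. The by-cohort displays in SAP 6.2.1 and 6.2.2 are descriptive, and SAP 5.2.1 lists no interval among descriptive statistics. That is fair: the reading comes from taking 2.3, 5.2 and 6.2 together. It is the natural reading, but it is an inference.

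Third, a reader might infer that every bootstrap fails at n=3. That goes too far. A symmetric studentised bootstrap reaches about 93% under normal data, and even the equal-tailed version reaches 83% under uniform data. The SAP describes neither; using the distribution of the mean itself fits the percentile type best.

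Fourth, the 25% figure does not carry over to all endpoints. The mini-dystrophin-specific measures (LEMP peptide and the specific antibody) have nil baseline by design, so a symmetric null change does not arise. It suits total dystrophin.

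Fifth, a cutoff at n ≤ 3 is partly convention: simulated percentile coverage at n=4 is still only about 80% under normal data. That stands, but no group in SAP 2.5 has four participants, and the cutoff matches the SAP's own plot rule.

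**Conclusion.** The point holds, conditionally. If the bootstrap interval is printed for the low-dose cohort or the non-ambulatory population and is of percentile type, it is exactly the sample range. Its label says 95%, but its coverage is at most 75% for a continuous outcome, and 72% or 64% under the two lognormal assumptions. The 75% ceiling needs only three independent values from a continuous distribution; the lower figures depend on the assumed skew. For total dystrophin with a symmetric null change, zero would be excluded about 25% of the time.

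The importance is minor. The endpoints are secondary, SAP 5.1 rules out formal hypothesis testing, and individual values are plotted. A reader might infer that dose escalation or a conclusion about efficacy rests on these intervals; no visible decision rule uses them. The harm is confined to reported precision in two small groups.

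**What to change.** In SAP 5.2 and 6.2, state that any group with n ≤ 3 at a visit gets listed individual values with minimum and maximum, and no bootstrap interval. This matches the box-plot rule in 6.2.1 and 6.2.2. If the text cut from 5.1 and 5.2 already says so, confirm that it covers n=3 as well as smaller groups, and that it covers these intervals.

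Name the interval type for the larger groups, so that the choice is fixed in advance. If it is percentile, note that coverage stays somewhat below 95% (about 92–93% at N=16 to 22 under normal data, lower under strong skew).

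The cost is two or three sentences. Groups of three or fewer lose an interval that, in percentile form, adds nothing to the minimum and maximum that SAP 5.2.1 already prints. The analysis of the larger groups is unchanged apart from the method being named.

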5.2.1. Analyses for Continuous Endpoints

For continuous variables, the data will be summarized using the number of participants, mean, median, SD, minimum, maximum.

5.2.2. Analyses for Categorical Endpoints

For categorical or ordinal variables, number of participants, numbers and percentages of participants meeting the categorical criteria will be supplied.

5.2.3. Analyses for Time-to-Event Endpoints

Time-to-event endpoints will be summarized using the Kaplan-Meier method (Kaplan and Meier 1958⁴) and estimated time-to-event-free curves will be displayed graphically when appropriate. Graphs will describe the number of participants at risk over time. The median, quartiles, and probabilities of an event at particular points in time will be estimated by the

Kaplan-Meier method. CIs for medians and quartiles are based on the Brookmeyer-Crowley method. CIs for the estimated probability of an event at a particular time point will be generated using the Greenwood formula.

5.3. Methods to Manage Missing Data

In listings, values below the LLOQ will be reported as "<LLOQ", where LLOQ will be replaced with the value for LLOQ for the corresponding assay.

5.3.1. Safety endpoints

[figure not shown]
For the analysis of safety endpoints, the sponsor data standard rules for imputation will be applied.

5.3.2. Immunogenicity endpoints

For immunogenicity assay results including ADA titers, NAb titers, and ELISpot levels, values below the LLOQ will not be imputed for summary statistics.

5.3.3. Secondary pharmacodynamic endpoints

Treatment induced mini-dystrophin levels below the LLOQ quantified by LC-MS assay (LEMP peptide or LLQV peptide) will be imputed as 0.5*LLOQ for summary statistics and graphical presentation.

5.3.6. Missed visits or Assessments out of Protocol-specified Visit Windows

To minimize missing data, unplanned measurements will be included in analyses unless otherwise specified. For summary analyses at scheduled visits, extended time windows for measurements specified in Appendix 2 will be implemented in analysis. If multiple values are observed within a time window, the value closest to the target visit day from the administration of fordadistrogene movaparvovec will be included in the analysis unless specified otherwise. Day 1 is defined as the study drug dosing visit.

6. ANALYSES AND SUMMARIES

6.1. Primary Endpoints

The safety and other endpoints detailed in Section 3.1 will be listed and summarized, where the resulting data presentations will consist of participants from the Safety Analysis Set (as defined in Section 4).

Primary safety analyses will be based on the data through 1-year post-treatment of fordadistrogene movaparvovec. Secondary safety analyses will be based on the long-term follow up data through 5-years post-treatment of fordadistrogene movaparvovec. Adverse events, ECGs, vital signs, physical and neurological examinations, cardiac MRI (or echocardiogram) and safety laboratory data will be reviewed and summarized on an ongoing basis during the study to evaluate the safety of participants. Safety data will be presented in tabular and/or graphical format and summarized descriptively, where appropriate. Analysis windows for these summaries and graphical displays by visit are provided in Appendix 2.

All analyses will be conducted by dose cohort and ambulatory status at baseline to evaluate the safety and tolerability of administering fordadistrogene movaparvovec.

6.1.1. Adverse Events

Incidence and severity of TEAEs will be reported.

Deaths and SAEs will be listed. The following will be summarized by dose cohort and ambulatory status at baseline:

- Incidence and severity of TEAEs (all causalities and treatment-related)
- Withdrawals due to TEAEs; and
- Incidence of SAEs (all causalities and treatment-related).

To evaluate the safety of sirolimus:

The incidence and severity of TEAEs (all causalities and treatment-related) relative to the initiation of treatment with sirolimus through 30 days post-last dose of sirolimus (approximately 44 days post-fordadistrogene movaparvovec infusion per sirolimus administration schedule) will be summarized for those participants who received sirolimus (sirolimus cohort) versus those who did not (non-sirolimus cohort).

No summaries will be provided by sirolimus cohort status since only one participant received sirolimus.

6.1.2. Laboratory Data

Central and local laboratory results will be combined for reporting purposes. Baseline is as defined in Section 3.1.2. Laboratory data including hematology, chemistry and urinalysis will be listed. If there is a local and central laboratory collection on the same day, the central laboratory value will be used for analysis.

The following will be summarized by dose cohort and ambulatory status at baseline. To evaluate the safety of sirolimus, the incidence and magnitude of abnormal laboratory findings through 30 days post the last dose of sirolimus administration will be summarized by sirolimus cohort (sirolimus, non-sirolimus) if there are at least 3 participants in each cohort. No summaries will be provided by sirolimus cohort status since only one participant received sirolimus.

• Incidence of laboratory test abnormalities without regard to baseline abnormality, for normal baseline, and for abnormal baseline.

For select laboratory parameters, data will be summarized by visit descriptively in tabular format and displayed graphically as described below.

Parameter	Presentation			
	Table: Shift table: Graph, Box-plo			
	Changes and Percent	<lln*,< td="">Changes from	</lln*,<>	Changes from	
	changes from baseline	Normal*,	baseline	
	By visit	>ULN	By visit	
		By visit		
GLDH	X	X	X	
CK	X	X	X	
C3 and C4	X		X	
Platelets	X		X	
Creatinine	X		X	

^{*}If the normal range is \leq or \leq ULN without the LLN, then the category \leq LLN will not be presented.

The shift tables will use baseline values categorized as < LLN, Normal, and > ULN, with the shifts being shown into the same categories.

For laboratory parameters summarized descriptively, if the raw laboratory values are obtained using different normal ranges over time or across participants, external normalized values that are normalized to pediatric textbook ranges will be used to summarize the results.

To assess the effect of sirolimus on complement activation, the C4 levels and platelet levels will be summarized descriptively and/or graphically by sirolimus cohort if there are at least 3 participants in each cohort as follows:

- Percent change from baseline to nadir through Day 30 post-fordadistrogene movaparvovec infusion
- Summary statistics including the mean, the location, the location shift between the sirolimus cohort and non-sirolimus cohort, and the corresponding 95% CI (when n ≥ 3) over time and at nadir based on the Hodges-Lehmann method (Hodges & Lehmann, 1963⁵; Hodges Jr & Lehmann 1983⁶).

The nadir is defined as the lowest measurement observed between baseline through Day 30 visit post-fordadistrogene movaparvovec infusion.

No summaries will be provided by sirolimus cohort status since only one participant received sirolimus.

cTn-I:

Baseline values will be categorized as Normal (within Normal Range) and above ULN. The shifts in categories over time showing the number and percent of participants in each category will be presented.

The participants will be divided into two categories: those with baseline cTn-I \leq 99th percentile (ie, ULN) and those with baseline cTn-I > 99th percentile (ie, ULN). For Centaur assay, the cTn-I 99th percentile (ie, ULN) will be 0.03 ng/mL. The LLOQ is 0.03 and values below LLOQ will set to 0.029. For the Beckman assay, the cTn-I 99th percentile (ie, ULN) will be 19.8 ng/L. The LLOQ is 2.3 ng/L and values below LLOQ will be set to 2.29 ng/L.

For participants with baseline cTn-I > 99th percentile (ie, ULN):

- a. Count the number of post-baseline visits at which cTn-I was >3X baseline for each participant. Present the number and percentage of participants who had 0, 1, 2, or 3 visits at which cTn-I was >3X baseline.
- b. For post-baseline visits with cTn-I > 3X baseline, present descriptive summary statistics (mean, SD, median, Q1, Q3, minimum and maximum) for the maximum cTn-I level.

Graphical displays:

• Spaghetti plot including participants with ≥ 2 visit assessments post-baseline that are >3X baseline.

For participants with baseline cTn-I ≤ 99th percentile (ie, ULN),

- a. Count the number of post-baseline visits at which cTn-I was >3X 99th percentile (ie, ULN) for each participant. Present the number and percentage of participants who had 0, 1, 2, or 3 visits at which cTn-I was >3X 99th percentile (ie, ULN).
- b. For post-baseline visits with cTn-I >3X 99th percentile, present descriptive summary statistics (mean, SD, median, Q1, Q3, minimum and maximum) for the maximum cTn-I level.

Graphical displays:

• Spaghetti plot including participants with ≥ 2 visit assessments post-baseline that are $> 99^{th}$ percentile (ie, ULN).

All visits (ie, planned and unplanned) will be included in these analyses.

Analysis windows for these summaries and graphical displays by visit are provided in Appendix 2.

Hepatotoxicity evaluation:

To assess potential liver injury, the eDISH plot will be used to present the liver safety data (Watkins et al., 2011⁷). Specifically, the peak AST or ALT (x-axis) and peak TBili (y-axis) will be shown as multiples of (x-fold or y-fold) the ULN on log scales displayed for each participant within a specific timeframe (week 52 for primary safety analyses). Four quadrants defined by the two lines corresponding to 3×ULN for peak AST or ALT and 2×ULN for peak TBili will be shown.

A separate listing displaying the following parameters over time will be generated for participants located in the right upper quadrant.

• ALT, AST, ALP, TBili, GGT, GLDH, CK, creatine kinase myocardial b fraction, platelets, Hepatitis A virus antibody and immunoglobulin M antibody, Hepatitis B virus surface antigen, Hepatitis C virus antibody, and Hy's Law criteria.

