Visit Number	Visit 1a,i	Visit	Visit 3 ^b	Visit 4b	Remote ^c	Visit	Remote ^c	Visit	Remote	Visit	Remotec	Visit	Remote ^c	Visit	Remotet
	Screening	2 ^{a,g}	Dosing +	Week 2	Visit 5	6	Visit 7	8 ^a	Visit 9	10	Visits	12ª	Visits 12.1	13 ^a	visits
		Baselin	24 Hour		Week 3	Wee	Week 6	Week	Week 10	Week	11.1,	Wee	and 12.2	Week	13.1, 14.1,
		e	Monitor-			k 4		8		12	11.2, 11.3	k 26	Weeks 32,	52	15.1, 16.1;
			ing +								Weeks		39		Years 1.5,
			initial								15, 19, 22				2.5, 3.5, 4.5
			follow-up												Visits 14-17 ^a
															Years 2-5
															/Early
															Termination
															(ET)
Visit Window	Day -196	Day -16	Day 1,	Day 14	Day	Day	Day	Day	Day	Day	Days	Day	Days	Day	Remote
	to	g	Day 2	(±1 day)	21	30	45	60	75	90	106,	180	225, 270	360	Days 545,
	Day -17	(-12 to	(Discharge),		(±3	(±3	(±3	$(\pm 3$	(±3	(±3	135,	(±7	(±7 days)		910, 1275,
		+2	Days 4 ^j , 7,		days)	days	days)	days)	days)	days	155	days)		days	1640; Visit
		days)	10 (±1 day)))	(±7)	Days 730,
											days)				1095, 1460,
															1825
															(±30
															days)/ET

h. Vital signs will always consist of blood pressure, respiration rate, and heart rate, but body temperature will also be obtained with these measurements at the following timepoints: within 30 minutes before and approximately 30 minutes, 1, 2, 4, 8, and 24 hours after the start of the infusion, and on Days 4, 7, 10, 14 and 30. Body temperature at additional timepoints may be collected as clinically indicated.

k. Clinical safety labs are described in Table 1. Additional safety labs on Days 1 (pre-dose) through Week 8 will include CCl and will continue to be collected until within normal limits or return to baseline.

Period	Screening	Baseline	Treatment					1st Ye	ar Follow	-up					Long-Term Follow-up
															and/or Early Termination
Visit Number	Visit 1 ^{a,i} Screening	Visit 2ª,g	Visit 3 ^b Dosing +	Visit 4 ^b Week 2	Remote ^c Visit 5	Visit 6	Remote ^c Visit 7	Visit 8ª	Remote ^c Visit 9	Visit 10	Remote ^c Visits	Visit 12ª	Remote ^c Visits 12.1	Visit 13a	Remote ^t visits
	Streening	Baselin	24 Hour	,, con -	Week 3	Wee	Week 6	Week		-	11.1,	Wee	and 12.2	Week	13.1, 14.1,
		e	Monitor-			k 4		8		12	11.2, 11.3	k 26	Weeks 32,	52	15.1, 16.1;
			ing +								Weeks		39		Years 1.5,
			initial								15, 19, 22				2.5, 3.5, 4.5
			follow-up												Visits 14-17 ^a
															Years 2-5
															/Early
															Termination
					_				_	_			_		(ET)

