safety of PF-06939926, per availability of drug product. 2) Increased the duration of length of entire study given increase in number of subjects to be enrolled, which is helpful for investigators to set expectations as to when they can expect final study results, and increased duration of subject participation from approximately 5 years to 5.5 years, given the extended Screening window as per Amendment 2. 3) Addition of possible local laboratory samples to be collected and tested on Study Days 7-10 and extension of complement biomarker collection through Week 8, or perhaps longer if outside normal range, so as to ensure better understanding of possible changes in laboratory results during this period, as well as to allow for closer safety monitoring per communications between the investigators and sponsor. 4) Removed reference to "blood smear" in Schedule of Activities, Section 6.3-6.6 and Table 1, given that this not a separate test and is already part of the hematology panel since the start of the study. 5) Assessment of drug concentrations of PF-06939926 changed to a titer method, which will be used to adjust referenced doses. Use of the more precise titer assay was implemented per regulatory request. 6) Broadened flexibility to increase the dosages of the protocol required glucocorticoids just prior to (ie, methylprednisolone) and for at

			least 3-months following administration of PF-06939926 to explore whether increased doses may mitigate risk of adverse immune reactions.
		7)	Expanded the list of examples of medications that can be administered to treat or prevent adverse events to include immunosuppressants and complement inhibitors as these may be used to mitigate risk of complement activation.
		8)	Removed reference to a 6 milliliter (mL) vial of investigational product, PF-06939926, as the vial size will be increased; the fill volume will remain 5 mL, as reflected.
		C	
Amendment 5	20 July 2020	1.	Expanded study population to include non-ambulatory subjects with Duchenne muscular dystrophy (DMD), in an effort to broaden the safety evaluation of PF-06939926 in this patient population (Title page, Section 3.1, and as noted below),

[figure not shown]
- 1) Updated current therapies for DMD given recent regulatory approval of another exon-skipping medication, ie, VYONDYS 53[™] (Section 1.2.1).
- 2) Broadened Rationale for Selected Patient Population Section (1.4.3) to include non-ambulatory subjects.

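### C3/C4 means by visit after Week 8 can rest mainly on participants who have not yet recovered, because later complement sampling appears to depend on the result

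*SAP*

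**What the plan says.** **Collection.** Footnote k of the protocol's Schedule of Activities begins "Additional safety labs on Days 1 (pre-dose) through Week 8 will include"; the analyte names that follow are redacted. It then says that these labs "will continue to be collected until within normal limits or return to baseline". The clinical safety row carries superscript k from the dosing visit through Visit 8 (Week 8, Day 60) and a plain X from Visit 9 (Week 10, Day 75). The Amendment 4 entry in Appendix 3 records "extension of complement biomarker collection through Week 8, or perhaps longer if outside normal range". I use that entry only to identify the redacted analyte.

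**Analysis.** SAP 6.1.2 says: "For select laboratory parameters, data will be summarized by visit descriptively in tabular format and displayed graphically as described below". The table below that sentence marks C3 and C4 for change and percent change from baseline by visit and for a by-visit box plot of change. It does not mark them for the shift table that GLDH and CK receive. The period is long: "Primary safety analyses will be based on the data through 1-year post-treatment of fordadistrogene movaparvovec". The long-term analysis extends to five years.

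**Missing data.** SAP 5.3.1 says only "For the analysis of safety endpoints, the sponsor data standard rules for imputation will be applied". SAP 5.3.6 adds "To minimize missing data, unplanned measurements will be included in analyses unless otherwise specified". Neither visible passage deals with tests that stop because the result has recovered.

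**The concern.** A by-visit mean can be compared across visits only if presence at a visit does not depend on the value being averaged. Through Week 8, everyone is due for the additional labs. After Week 8, if footnote k covers C3 and C4, a participant stays in the table while his last value was abnormal and below baseline, and leaves it once he has recovered. The late means and box plots then describe mainly the slow or non-recovering participants, and the curve can make recovery look slower than it was.

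The protocol's sirolimus appendix ties complement activation to serious adverse events and describes a consistent early fall in C4. How long depletion lasts is therefore a fair safety question. The visible C3/C4 displays offer little to set against these means. There is no shift table, and the C4 nadir summary through Day 30 belongs to the sirolimus comparison, which will not be produced because only one participant received sirolimus. The cells are also small: SAP 2.5 gives 3, 16 and 3 participants by ambulatory status and dose. One or two participants could set a late-visit mean.

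**Working it through.** The plan states no figure to reproduce. The check has two parts.

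**1. Collection rule against analysis rule**

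| | Through Week 8 (Day 60) | After Week 8 |
|---|---|---|
| Protocol, footnote k | Additional labs for all | Only until normal or back at baseline |
| Schedule, clinical safety row | X with superscript k | Plain X |
| SAP 6.1.2, C3/C4 | Change by visit | Same display; no visible cut-off |

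With N participants, of whom r are still sampled at a visit:

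mean(sampled) − mean(all) = (1 − r/N) × [mean(sampled) − mean(released)]

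The gap is zero only if everyone is still sampled, or if sampled and released participants have the same mean change. A rule that releases participants on recovery tends to separate those two means.

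**2. Illustration of size**

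Only N = 22 (SAP 2.5) and the visit days (Schedule) come from the documents. The rest is assumed:

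- Baseline b = 100 × exp(normal, SD 0.25).
- Value on day d = b × [1 − 0.5 × 0.5^((d − 10)/h)], which is a 50% fall at Day 10.
- Half-life h has median 10, 20 or 40 days, log-SD 0.8.
- Measurement log-SD is 0.08, applied to baseline and to later values.
- Normal range is 65 to 150. Back at baseline means at least 95% of the measured baseline.
- All are measured at Day 60. Afterwards, a participant is measured until one value meets the rule, and that value is kept.

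There were 4,000 simulated cohorts per scenario. Cells show mean % change in all 22, then in those still sampled, then the average number sampled. All are averaged over cohorts with at least one participant still sampled.

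| Scenario | Day 90 | Day 180 |
|---|---|---|
| h = 10, normal or baseline | −1.7 / −11.8 (1.4) | 0.0 / −11.2 (1.1) |
| h = 20, normal or baseline | −6.0 / −17.1 (2.1) | −1.6 / −12.8 (1.3) |
| h = 40, normal or baseline | −13.8 / −23.8 (4.1) | −5.5 / −17.2 (2.0) |
| h = 20, baseline only | −5.9 / −13.6 (10.9) | −1.2 / −11.1 (5.2) |
| Stress A | −2.0 / −2.0 (6.0) | 0.1 / 0.1 (5.2) |
| Stress B | 20.0 / 20.1 (4.2) | 21.0 / 21.2 (3.1) |

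Both stress cases assume a 30% fall and release on the normal range only. Stress A has median h = 20 days with log-SD 0.3, baseline log-SD 0.4 and measurement log-SD 0.05. Stress B has a rebound 20% above baseline, median h = 10 days with log-SD 0.8, baseline log-SD 0.3 and measurement log-SD 0.10.

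In the first four scenarios, from Day 75 to Day 360, the sampled mean lay below the whole-cohort mean by between 13.2 − 7.9 = 5.3 points (baseline only, Day 75) and 17.0 − 4.7 = 12.3 points (h = 20, normal or baseline, Day 106). In the stress cases the two means differed by at most 0.4 points. There, participants stayed in the sample mainly because their own baseline lay low or high against the normal range, so sampled and released participants had nearly the same mean change.

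With fast recovery there is often no late mean at all. At h = 10, only 17% of simulated cohorts had anyone still sampled at Day 180.

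**The case against.** The strongest reply is that much of this turns on redacted text.

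- **Analyte.** Footnote k does not visibly name C3 or C4. The Amendment 4 entry speaks of complement biomarkers in general, and later amendments followed. Redacted tests in the protocol's Table 1, redacted Schedule rows, or the exploratory biomarker row (marked at Weeks 26 and 52) could hold complement samples due from everyone. This stands, so the link is probable and not established.
- **Visit limits.** SAP 6.1 and 6.1.2 send the reader to Appendix 2 for analysis windows, and that appendix is not shown. It could already end the C3/C4 display at Week 8. This stands too.
- **Week 12.** A reader might infer from protocol Section 6.8 that complement is no longer drawn at that visit, because the Table 1 labs are listed without the added item seen at Weeks 2 and 4. A further blood-sample bullet there is redacted, so the section does not settle the matter.
- **Visible n.** SAP 5.2.1 reports the number of participants, so a shrinking denominator would be seen. The number does not say that leaving meant recovery.
- **Small groups.** The SAP history for version 5 gives individual profiles for subgroups of fewer than 3, and a fragment in the current SAP 5.2 suggests that this survives. Whether it applies visit by visit is not stated.
- **Importance.** The acute complement changes fall well inside the period of scheduled sampling, and no formal decision rests on later means. That limits the consequence to how the duration of depletion is described.

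**Conclusion.** The point holds in conditional form. If footnote k governs C3 and C4, as is probable, and nothing redacted limits the display, then means and box plots after Week 8 can describe mainly non-recovered participants and can overstate lasting depletion. Results through Week 8 are not affected.

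A reader might go further and say that the later visits do overstate depletion, or by a given multiple. The documents do not support that. They contain no recovery data, and the illustration runs from almost no gap to about 12 percentage points, depending on the recovery pattern, the spread of baselines, and which of the two release criteria acts first. The simulation also pools all 22 participants, whereas the SAP reports by dose cohort and ambulatory status.

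The change is worth making because it is cheap and the affected displays are the only C3/C4-specific by-visit summaries visible in SAP 6.1.2.

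**What to change.** First state in SAP 6.1.2 whether C3 and C4 are scheduled for every participant after Week 8. If they are, or if Appendix 2 already ends these displays at Week 8, one sentence closes the point.

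Otherwise:

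1. Limit the C3/C4 by-visit mean tables and box plots to visits through Week 8 (Day 60).
2. For each later visit report, out of all dosed participants: n (%) not yet recovered; n (%) recovered, meaning a documented last value that is normal or back at baseline; and n (%) missing for other reasons, such as withdrawal or a missed visit.
3. Show individual profiles for those still sampled.
4. Add a table footnote giving the collection rule.

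The three categories must stay separate. Counting everyone no longer sampled as recovered would score withdrawn or missed participants as recovered and could hide persistent depletion.

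The cost is SAP wording and a small change to the table and plot shells. No new data are needed. The downside is that no mean C3/C4 is reported after Week 8.
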